### **1.2 Schedule of Analyses**

There are 2 planned database locks: (1) primary completion date (PCD) database lock, which occurs after the last subject completes the Week 12/End of Treatment (EOT) Visit of the Double-Blind Treatment (DBT) Phase; and (2) last subject last visit (LSLV) database lock, which occurs after the last subject completes the Follow-Up Week 2 Visit.

The PCD final CSR is produced after the PCD database lock. Analyses focus on efficacy and safety endpoints during the DBT Phase.

The LSLV final CSR is produced after the LSLV database lock. All endpoints are assessed.

No interim analyses are planned.

## **2 STUDY DESCRIPTION**

### **2.1 Study Design**

This is a multicenter, randomized, double-blind, placebo-controlled evaluation of the safety and efficacy of rimegepant 75 mg orally disintegrating tablet (ODT) taken every other day (EOD) for prophylaxis in adults with a history of inadequate response to a variety of available oral migraine-preventive medications from different mechanistic classes.

[figure not shown]

The study has 4 phases:

- Observation Phase (OP): Lasts approximately 28 days. Includes the Screening Visit and Pre-Randomization Evaluation Visit which must occur within 4 days of the Baseline Visit.
- DBT Phase:
  - Lasts up to 12 weeks, and includes the Baseline Visit, and Week 2, Week 4, Week 8, Week 12, and DBT EOT Visits.
  - Subjects are randomized 1:1 to 1 of the following 2 treatment groups at the Baseline Visit:
    - Rimegepant 75 mg dosed EOD
    - Placebo matching rimegepant 75 mg dosed EOD.
  - Randomization is stratified using a Randomization and Trial Supply Management (RTSM) system by (1) the number of migraine days reported to have occurred during the 28-day OP (4 to 7 or 8 to 14); and (2) the number of ROM medication categories with previous inadequate response (2 or 3 to 4). See Section 2.2.
    - Previous inadequate response is defined as lack of efficacy within 10 years of the Screening Visit, prior intolerance within 10 years of the Screening Visit, or contraindication.
  - All randomized subjects who discontinue early from the DBT Phase should complete the DBT EOT Visit. Otherwise, subjects should complete the Week 12 Visit.
- Open-label Extension (OLE) Phase:
  - Subjects who complete the DBT Phase and are in good standing may enter the OLE Phase. Subjects who (1) discontinue early from the DBT Phase or (2) have already entered the Follow-up Phase are not eligible to enter the OLE Phase.
  - Lasts up to 12 weeks, and includes the Week 14, Week 24, and OLE EOT Visits.
  - Subjects take rimegepant 75 mg dosed EOD.
  - All randomized subjects who discontinue early from the OLE Phase should complete the OLE EOT Visit. Otherwise, subjects should complete the Week 24 Visit.
- Follow-up Phase
  - Lasts up to 2 weeks, and includes the Follow-up Week 2 Visit primarily for safety assessments. The visit should occur approximately 2 weeks after the last visit in the last treatment phase, i.e., (i.e., Week 12/DBT EOT Visit if the subject did not enter the OLE Phase; Week 24/OLE EOT Visit if the subject entered the OLE Phase).
  - All randomized subjects should complete the Follow-up Week 2 Visit, regardless of completing the DBT or OLE Phase, except those who discontinue early from the DBT or OLE Phase due to withdrawal of consent, death, or lost to follow-up.

The design of the study is shown in Figure 1. Approximately 1000 subjects are enrolled in order to randomize approximately 600 subjects.

**Figure 1 Study Schematic**

## 2.2 Treatment Assignment

The RTSM system assigns a subject identifier number at the Screening Visit.

The RTSM system randomizes eligible subjects to treatment groups (see Section 2.1) using permuted blocks of size 6 within each of the 4 randomization strata at the Baseline Visit. Randomization is stratified by (1) the number of migraine days reported to have occurred during the 28-day OP (4 to 7 or 8 to 14); and (2) the number of ROM medication categories with previous inadequate response (2 or 3 to 4).

The RTSM system also assigns specific container numbers for study drug to be dispensed at the Baseline Visit and subsequent visits in the DBT and OLE Phases.

## 2.3 Blinding and Unblinding

This study is blinded to treatment group through the PCD database lock (see Section 1.2). Draft TLFs for the PCD Final CSR are produced with dummy treatment groups prior to the PCD database lock. Otherwise, TLFs for the PCD Final CSR and LSLV Final CSR are produced unblinded.

## 2.4 Protocol and Protocol Amendments

C4951012 SAP Version 1 is based on C4951012 Protocol Version 4 (01-Mar-2023). Note that Protocol Version 4 added the OLE Phase. The study was originally designed with the Observation, DBT, and Follow-Up Phases.

C4951012 SAP Versions 2, 3, and 4 are based on C4951012 Protocol Version 5 (09-Aug-2023). Protocol changes that affected statistical analyses were the following: changing the sponsorship to Pfizer; removing ECG collection at Week 14; stating that there are 2 planned database locks and 2 final CSRs; using robust standard error (SE) estimation methods; excluding subject as a random effect from linear mixed effects models; replacing Cochran-Mantel-Haenszel test with Mantel-Haenszel risk estimation; and modifying exclusion criteria, which affects relevant protocol deviations.

C4951012 SAP Version 5, 6, 7, 8, and 9 are based on C4951012 Protocol Version 7 (31-Aug-2024).

### **3 STUDY OBJECTIVES AND ESTIMANDS**

#### **3.1 Objectives**

A month is defined as 4 weeks (28 days) for the purpose of this protocol.

##### **3.1.1 Primary Objective**

To compare the efficacy of rimegepant to placebo as an EOD dosing regimen for prophylaxis in adults with a history of inadequate response to agents across 2 to 4 categories of ROM medications as measured by the mean reduction from the OP in the number of migraine days per month over the entire DBT Phase.

##### **3.1.2 Secondary Objectives**

###### **3.1.2.1 Key Secondary Objectives**

1. To compare the proportion of subjects with  $\geq 50\%$  reduction from the OP in the number of migraine days of moderate or severe headache pain intensity per month over the entire DBT Phase (Weeks 1 to 12) between rimegepant and placebo.
2. To compare the mean reduction from the OP in the number of migraine days per month in the first 4 weeks of the DBT Phase between rimegepant and placebo.
3. To compare the mean reduction from the OP in the number of migraine days per month in the last 4 weeks of the DBT Phase between rimegepant and placebo.
4. To compare the mean change from baseline in the Migraine-Specific Quality-of-Life Questionnaire v 2.1 (MSQ) restrictive role function domain score at Week 12 of the DBT Phase between rimegepant and placebo.
5. To compare the mean change from baseline in Migraine Interictal Burden Scale (MIBS) score at Week 12 of the DBT Phase between rimegepant and placebo.

### **3.1.2.2      *Other Secondary Objectives***

1. To evaluate the frequencies of adverse events (AEs) by intensity, serious adverse events (SAEs), AEs leading to study drug discontinuation, and Grade 3 to 4 laboratory test abnormalities during the DBT and OLE Phases.
2. To evaluate the proportion of subjects with  $\geq 50\%$  reduction from the OP in the number of migraine days (regardless of headache pain intensity) per month over the entire DBT Phase (Weeks 1 to 12) in rimegepant and placebo.
3. To evaluate the mean number of acute migraine medication days per month in each month and over the entire DBT Phase in rimegepant and placebo.
4. To evaluate the mean change from baseline in Migraine Interictal Burden Scale (MIBS) score over time in the DBT Phase in rimegepant and placebo.
5. To evaluate the mean change from baseline in MSQ domain scores (restrictive role function domain, preventive role function domain and emotional function domain) over time in the DBT Phase in rimegepant and placebo.
6. To evaluate the mean change from baseline in the Migraine Functional Impact Questionnaire (MFIQ) scores (physical function, usual activities, social function, overall impact on usual activities, and emotional function) over time in the DBT Phase in rimegepant and placebo.
7. To evaluate the mean change from baseline in the Work Productivity and Activity Impairment (WPAI) – Migraine scores (absenteeism, presenteeism, work productivity loss, and activity impairment) over time in the DBT Phase in rimegepant and placebo.
8. To evaluate the mean change from baseline in the Patient Global Assessment (PGA) – Migraine score over time in the DBT Phase in rimegepant and placebo.

### **3.1.1      *Exploratory Objectives***

1. To evaluate the mean reductions from the OP in the number of migraine days per month and number of headache days per month by headache pain intensity (total; moderate or severe) in each month and the entire course of the DBT Phase in rimegepant and placebo.
2. To evaluate the proportions of subjects with  $\geq 30\%$  reduction,  $\geq 50\%$  reduction,  $\geq 75\%$  reduction, and 100% reduction from the OP in the number of migraine days per month and number of headache days per month by headache pain intensity (total; moderate or severe) in each month and over the entire DBT Phase in rimegepant and placebo.
3. To evaluate the mean reductions from the OP in the number of migraine days per week and number of headache days per week by headache pain intensity (total; moderate or severe) in each week of the first 4 weeks of the DBT Phase in rimegepant and placebo.

4. To evaluate the proportions of subjects with  $\geq 50\%$  reduction from the OP in the number of migraine days per week and number of headache days per week by headache pain intensity (total; moderate or severe) in each week of the first 4 weeks of the DBT Phase in rimegepant and placebo.
5. To evaluate the proportions of subjects with a migraine day and headache day by headache pain intensity (total; moderate or severe) on each day of the first week of the DBT Phase in rimegepant and placebo.
6. To evaluate the median time to  $\geq 30\%$  reduction and  $\geq 50\%$  reduction from the OP in the number of migraine days per month and number of headache days per month by headache pain intensity (total; moderate or severe) in the DBT Phase in rimegepant and placebo.
7. To evaluate the mean number of acute migraine medication days per month in each month and over the entire DBT Phase in rimegepant and placebo.
8. To evaluate the mean change from baseline in the Headache Impact Test (HIT-6) score over time in the DBT Phase in rimegepant and placebo.
9. To evaluate the proportion of subjects with  $\geq 5$ -point reduction from baseline in the HIT-6 score over time in the DBT Phase in rimegepant and placebo.
10. To evaluate the mean changes from baseline in the MSQ domain, MIBS, WPAI – Migraine, HIT-6 and PGA scores over time in the OLE Phase.
11. To evaluate the proportion of subjects with  $\geq 5$ -point reduction from baseline in the HIT-6 score over time in the OLE Phase.
12. To evaluate the frequencies of hepatic-related AEs and hepatic-related AEs leading to study drug discontinuation during the DBT and OLE Phases.
13. To evaluate the frequency of liver function test (LFT) elevations (AST, ALT, or total bilirubin) based on fold changes above ULN during the DBT and OLE Phases.
14. To evaluate the Columbia-Suicide Severity Rating Scale (C-SSRS) during the DBT and OLE Phases.

### 3.2 Estimands

An estimand is the target of estimation to address the scientific question of interest posed by a study objective. The 4 attributes of an estimand include the population of interest, endpoint of interest, summary of the endpoint, and specification of how intercurrent events are reflected in the scientific question of interest.

For all objectives, the population of interest is defined through appropriate inclusion/exclusion criteria to reflect the targeted patient population for approval. Refer to the protocol for inclusion/exclusion criteria.

## **Intercurrent Events**

Intercurrent events are those that occur after treatment initiation and either preclude observation of the endpoint or affect its interpretation.

Study drug discontinuation before the time point of interest defining the endpoint is considered an intercurrent event.

- For efficacy objectives assessed with a continuous endpoint, study drug discontinuation is handled with a “hypothetical strategy,” i.e., the hypothetical scenario is that had subjects not discontinued study drug, their efficacy would have been similar to the efficacy of subjects from the same treatment group and randomization stratum who did not discontinue study drug. All observed values of the endpoint of interest are excluded after study drug discontinuation plus 1 day (see Section 7.2), and statistical methods are used to estimate the treatment effect that would have been seen had the intercurrent event not occurred.
- For efficacy objectives assessed with a binary or time-to-event endpoint, study drug discontinuation is handled with a “composite strategy,” i.e., the occurrence of the intercurrent event is integrated as a component of the endpoint. All observed values of the endpoint of interest are excluded after study drug discontinuation plus 1 day (see Section 7.2). Subjects with missing data are considered failures for binary endpoints. Subjects who achieve the response criteria before study drug discontinuation are considered to have an event for time-to-event endpoints.
- For safety objectives, study drug discontinuation is handled with a “while-on-treatment strategy,” i.e., response to treatment prior to the occurrence of the intercurrent event of interest, such that all observed values of the endpoint of interest are used prior to study drug discontinuation plus 7 days (see Section 7.2 and the Core SAP).
- For outcomes research objectives, study drug discontinuation is handled with a “treatment policy strategy,” i.e., the occurrence of the intercurrent event is considered irrelevant, such that all observed values of the endpoint of interest are used regardless of study drug discontinuation.

Nonstudy prophylactic migraine medication use before the time point of interest defining the endpoint is also considered an intercurrent event. For all objectives, this intercurrent event is handled with a treatment policy strategy, such that all observed values of the endpoint of interest are used. Note, in general, that nonstudy prophylactic migraine medication use is prohibited during the study.

Nonstudy acute migraine-specific medication use before the time point of interest defining the endpoint is also considered an intercurrent event, except for efficacy objectives based on acute migraine-specific medication days or acute migraine medication days.

- For efficacy objectives based on migraine days or headache days, this intercurrent event is handled with a composite strategy, such that acute migraine-specific medication use is part of the endpoint definition of migraine days and headache days.

- For safety and outcomes research objectives, this intercurrent event is handled with a treatment policy strategy, such that all observed values of the endpoint of interest are used.

Use of nonstudy other medication to treat headache (migraine or nonmigraine) or aura before the time point of interest defining the endpoint is also considered an intercurrent event, except for the efficacy objective based on acute migraine medication days.

- For efficacy objectives based on headache days, this intercurrent event is handled with a composite strategy, such that medication use is part of the endpoint definition of headache days.
- For all other efficacy, safety, and outcomes research objectives, this intercurrent event is handled with a treatment policy strategy, such that all observed values of the endpoint of interest are used.

See Section 4.1 for analysis sets that are used to assess endpoints.

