Procedure	Screening Visit	Observation Phase ¹ (28 days, + 3 days)	Pre-Randomization Evaluation Visit: must occur within 4 days of Baseline (Randomization) Visit (+2 days) ²	Baseline (Randomization) Visit ² (Day 1)	Week 2 Visit ⁶ (Day 15 +/- 2 days)	Week 4 Visit ⁶ (Day 29 +3 days)	Week 8 Visit ⁶ (Day 57 + 3 days)	Week 12 Visit (Day 86 +3 days) / End of Treatment (EOT) ^{3,8} Visit for early discontinuation	NOTES
Visit	V1	-	V2	V3	V4	V5	V6	V7	
Migraine Functional Impact Questionnaire (MFIQ) ⁵				X				→ X	Completed by the subject on the handheld eDiary every 7 days.

- While on-study, all visit windows are used for scheduling purposes and all efforts should be made to return subjects to the 28-day schedule if scheduling changes are made at any previous visit(s). NOTE: migraine days, headache days and non-migraine headache days reported during the “+3 days” window will not be used for determining eligibility.
- The duration between the Pre-randomization Evaluation Visit and the Baseline Visit is 4 days. The “+2” days window is included *for scheduling purposes only*. Every effort should be made to collect the Pre-randomization Evaluation Visit samples as close to, and within, the 4 days prior to the Baseline Visit as possible. However, for scheduling convenience, this window may be up to 6 days (between the Pre-randomization Evaluation Visit and the Baseline Visit).
- Randomized subjects who discontinue early from the DBT Phase should complete the EOT Visit, except in the case of withdrawal of consent, loss of a subject’s ability to consent freely, death, or when a subject is lost to follow-up. Otherwise, subjects should complete the Week 12 Visit.
- Patient Global Assessment (PGA) will be programmed on the subject handheld device and completed by the subject daily.
- Migraine Functional Impact Questionnaire (MFIQ) will be programmed on the subject handheld device every 7 days. Subject will have a “+1” day window allowing the subject a total of 48 hours to complete the MFIQ.

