4.3.5. Follow-up Phase

All randomized subjects should complete the Follow-up Week 2 Visit, except those who discontinue early from the study due to withdrawal of consent, loss of a subject's ability to consent freely, death, or when a subject is lost to follow-up.

The Follow-up Phase will have one scheduled visit at Follow-up Week 2 for targeted safety assessment and end-of-study procedures. At this visit, subjects will undergo the follow-up visit procedures as detailed in Table 1 for those subjects that either discontinue early from the DBT Phase or do not enter the OLE Phase, and Table 2 for those subjects completing or discontinuing early from the OLE Phase. In addition, compliance with the concomitant medication paper diary will be assessed. Investigators should assess subjects for AEs consistent with drug dependency or withdrawal effects and report as appropriate (see Section 7.4).

The Follow-up Week 2 Visit is to occur approximately 2 weeks (14 days +/- 2 days) after the last visit in the last treatment phase (i.e., Week 12/DBT EOT Visit if the subject did not enter the OLE Phase; Week 24/OLE EOT Visit if the subject entered the OLE Phase).

Subjects will continue to record all concomitant medications, including standard of care acute migraine medications (both prescribed and OTC), taken during the Follow-up Phase in the Concomitant Medication paper diary.

Due to the COVID-19 Pandemic, some selected study visits may be conducted remotely (Ex: Telephone, telemedicine) and must be documented within the source records as being conducted remotely. All procedures not able to be completed due to a visit being conducted

remotely must be reported as a protocol deviation and can be performed at the next visit, where appropriate to do so based on subject participation.

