#### 6.4.1.5 On-DB or OL Rimegepant AEs

Frequency tables of on-DB or OL rimegepant AEs are provided for the DB or OL rimegepant safety analysis set by SOC and PT for the following endpoints:

- AEs by worst intensity (other secondary objective #1)
- SAEs (other secondary objective #1)
- Exposure-adjusted multiple occurrences of unique AEs.

Calculations for on-DB or OL rimegepant exposure-adjusted multiple occurrences of unique AEs use an analysis period reference start date = DB or OL rimegepant start date, analysis period reference end date = DB or OL rimegepant last date + 7 days if the DB or OL rimegepant last date is nonmissing, and analysis period reference end date = last contact date if the DB or OL rimegepant last date is missing.

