## 6.4.2 Laboratory Tests

Laboratory tests are analyzed using results from local laboratory tests reported on CRFs and the external central laboratory Medpace. TLFs display results in both Systeme Internationale (SI) and United States (US) units, if applicable.

Laboratory tests of clinical interest are collected at the following visits:

- Hematology: Screening; Pre-Randomization; Weeks 12/EOT, 14, and 24/EOT
- Serum chemistry: Screening; Pre-Randomization; Weeks 12/EOT, 14, and 24/EOT.  
Exceptions are for the following:
  - LFTs (ALT, AST, alkaline phosphatase [ALP], TBL, direct bilirubin, indirect bilirubin):  
Screening; Pre-Randomization; Weeks 4, 12/EOT, 14, and 24/EOT.

The following by-subject laboratory test listings are provided for the enrolled analysis set:

- Laboratory test results using the Common Technical Criteria for Adverse Events/Division of Acquired Immune Deficiency Syndrome (CTCAE/DAIDS) toxicity grading scale (SI units). The listing displays all test results over time for subjects with grade 3 to 4 laboratory test abnormalities at any time point.
- Laboratory test results using the Food and Drug Administration (FDA) toxicity grading scale (US units). The listing displays all test results over time for subjects with grade 3 to 4 laboratory test abnormalities at any time point.
- LFT values and ratios to ULN (i.e., ALT, AST, TBL and ALP) (SI units). The listing displays all LFT results over time for subjects with select LFT elevations (ALT or AST > 3x ULN; ALP or TBL > 2x ULN) at any time point.
- Pregnancy test results (SI units). The listing displays all pregnancy test results over time for subjects with a positive pregnancy test at any time point.

Refer to the protocol for laboratory tests of clinical interest. Refer to the Core SAP for toxicity grades and TLF contents.

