### 6.4.2.1 Laboratory Test Abnormalities

Frequency tables of the worst (highest) laboratory test abnormality for each graded laboratory test are provided for the following safety analysis periods and analysis sets:

- On-DBT for the DBT safety analysis set
- On-OL rimegepant for the OL rimegepant safety analysis set.

Grade 3 to 4 results support other secondary objective #1.

Frequency tables of laboratory test shift from baseline to the worst abnormality for each graded laboratory test are provided for the following safety analysis periods and analysis sets:

- On-DBT for the DBT safety analysis set

- On-OL rimegepant for the OL rimegepant safety analysis set

Separate tables are provided for each toxicity grading scale: CTCAE/DAIDS using SI units; and FDA using US units.

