## 7 CONVENTIONS

### 7.1 Derived Dates

Derived dates are defined as follows:

- Screening visit date: earliest visit date containing “screening” in the visit label from the Date of Visit CRF
- eDiary measurement date: complete datepart{eDiary finding date/time} – 1 day, if from the eDiary headache log; complete datepart{eDiary finding date/time} otherwise
- eDiary efficacy data date: eDiary measurement date from the eDiary headache log
- Study drug start date: earliest complete dosing date from IP Dosing Wallet 1 to 4 and Replacement IP Dosing Wallet 1 to 4 CRF records with number of tablets taken  $>0$ . This is an analysis period reference date.
- Study drug end date: latest complete dosing date from IP Dosing Wallet 1 to 4 and Replacement IP Dosing Wallet 1 to 4 CRF records with number of tablets taken  $>0$
- Study drug last date:

- Before the LSLV database lock: study drug end date derived only for subjects who have either (1) or (2):
  - (1) “yes” or “no” response to the phase completion question on the DB Subject Status CRF, and either of the following:
    - ❖ “no” response to the continuing to the next phase question on the DB Subject Status CRF
    - ❖ {“Follow-up” specified as the next phase on the DB Subject Status CRF} and missing OL rimegepant start date
  - (2) “yes” or “no” response to the phase completion question on the OLE Subject Status CRF

- LSLV database lock: study drug end date

This is an analysis period reference date.

- DB study drug start date: earliest complete dosing date from IP Dosing Wallet 1 to 4 and Replacement IP Dosing Wallet 1 to 4 CRF records with number of tablets taken per day >0 and valid DB wallet ID. This is an analysis period reference date.
- DB study drug end date: latest complete dosing date from IP Dosing Wallet 1 to 4 and Replacement IP Dosing Wallet 1 to 4 CRF records with number of tablets taken per day >0 and valid DB wallet ID
- DB study drug last date:
  - Before the PCD database lock: DB study drug end date derived only for subjects with “yes” or “no” response to the phase completion question on the DB Subject Status or OLE Subject Status
  - PCD database lock and after: DB study drug end date

This is an analysis period reference date.

- OL rimegepant start date: earliest complete dosing date from IP Dosing Wallet 1 to 4 and Replacement IP Dosing Wallet 1 to 4 CRF records with number of tablets taken per day >0 and valid OL wallet ID. This is an analysis period reference date.

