  - DBT outcomes research: This period is used to assess outcomes research endpoints during the DBT Phase for the DBT efficacy analysis set.
  - OL rimegepant outcomes research: This period is used to assess outcomes research endpoints during the OLE Phase for the DBT efficacy analysis set.

For endpoints marked with “\*”, refer to the Core SAP for the definitions of analysis periods in Phase 2/3/4 multiple-dose studies with both DBT and OLE Phases. See Section 7.1 for derived dates for determining analysis periods.

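### An early-discontinuation EOT sample drawn more than 7 days after the last dose falls into follow-up, where the SAP plans no graded-laboratory or C-SSRS table

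*SAP*

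**What the plan says.** SAP 3.2 (Intercurrent Events) handles study drug discontinuation for safety objectives with a while-on-treatment strategy: "all observed values of the endpoint of interest are used prior to study drug discontinuation plus 7 days". The anchor is a dose, not a visit. SAP 7.1 gives "DB study drug end date: latest complete dosing date from IP Dosing Wallet 1 to 4", and SAP 7.2 assigns measurements to periods by comparing their dates with the period reference dates.

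The laboratory schedule in SAP 6.4.2 is "Hematology: Screening; Pre-Randomization; Weeks 12/EOT, 14, and 24/EOT". Serum chemistry has the same schedule, except that LFTs are also drawn at Week 4. Of the graded tables, SAP 6.4.2.1 says "Grade 3 to 4 results support other secondary objective #1"; it plans them for the on-DBT and on-OL rimegepant periods only. SAP 6.4.5 does the same for the C-SSRS.

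On the early visit, protocol 4.3 (Table 1 footnotes) says "Randomized subjects who discontinue early from the DBT Phase should complete the EOT Visit, except in the case of withdrawal of consent", followed by further exceptions. Neither that footnote nor protocol 4.3.3 or 6.6 says how soon after the last dose the visit takes place. The later safety visit is counted from a visit as well: "The Follow-up Week 2 Visit is to occur approximately 2 weeks (14 days +/- 2 days) after the last visit in the last treatment phase" (protocol 4.3.5).

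**The concern.** The analysis window is measured from the last dose, while the visit that supplies the sample is not. Whether an early stopper contributes to the placebo-controlled laboratory comparison then depends on how quickly that subject returned to the site. Subjects who stop for adverse events are among those a safety reader most wants to see, and promptness of return could differ between arms.

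Grade 3 to 4 laboratory abnormalities are a named other secondary endpoint. A table that drops such subjects without saying so would show a smaller denominator and no reason for it. The C-SSRS has an added twist. After screening its recall runs since the last visit, so an EOT assessment made on day 10 after the last dose still covers days on drug, yet its date places it in follow-up.

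**Working it through.** The plan states no figure of its own on this point, so the check sets the rules side by side.

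**1. The cut-off.** Let g be the number of days from the last double-blind dose to the sample. The 7-day limit appears in four places that agree:
- SAP 3.2, as quoted.
- SAP 6.4.1.5, where the reference end date is "DB or OL rimegepant last date + 7 days if the DB or OL rimegepant last date is nonmissing".
- SAP 4.1, where the interim safety set needs a gap of more than 7 days.
- SAP Table 6, where the first follow-up window opens at follow-up day 8.

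So a sample with g up to 7 is on-DBT and one with g of 8 or more is not. A subject who discontinues the DBT Phase early cannot enter the OLE (protocol 4.3.3), so the period that receives the sample is follow-up.

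**2. Does the EOT label rescue it?** Not on the visible text. SAP 7.2 slots by date. The Table 6 footnote uses visit labels only for subjects outside the full analysis set, and only for pretreatment visits.

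**3. Can g exceed 7?** After Week 4 the scheduled visits are Day 29, Day 57 and Day 86 (protocol Table 1). Take a subject dosed from Day 1 every other day who stops at home after the Day 35 dose (29 + 3 × 2 = 35). The on-DBT window ends on Day 35 + 7 = 42. If the stop comes to light at the Week 8 visit, g = 57 − 35 = 22 days. A regular Week 12 visit has the same problem if dosing stopped more than 7 days before it.

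**4. What else could supply the value, and which table receives a late one?**

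| Parameter | Scheduled post-dose in DBT | Scheduled at Follow-up Week 2 | Follow-up frequency table |
|---|---|---|---|
| Haematology, non-LFT chemistry | Week 12/EOT | No | No (SAP 6.4.2.1) |
| C-SSRS | Week 4, Week 12/EOT | No | No (SAP 6.4.5) |
| LFT elevations | Week 4, Week 12/EOT | No | Yes (SAP 6.4.2.2) |
| ECG | Week 12/EOT | No | Yes (SAP 6.4.4.2) |
| Vital signs | Weeks 2, 4, 8, 12/EOT | Yes | Yes (SAP 6.4.3.2) |

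The LFT and ECG rows are telling. Neither is scheduled at the Follow-up visit, so their follow-up tables can be filled only by late EOT or unscheduled measurements. Haematology, other chemistry and the C-SSRS are in the same position without a table.

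**5. Effect on the rate.** SAP Table 3 restricts the laboratory summary to subjects with on-treatment laboratory data. If an arm has n treated subjects, m of them with no on-DBT value, and x of the rest with a Grade 3 to 4 result, the table shows x/(n − m). The m subjects are in neither part, and the on-DBT shift table loses them too.

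**6. Size.** The documents give no rate of early stopping and no distribution of g. For illustration only, assume that 5% to 20% of 600 stop early: 600 × 0.05 = 30 to 600 × 0.20 = 120. The upper end equals 600 − 480, the number not expected to enter the OLE, which also includes completers who decline or are ineligible. Assume further that 10% to 50% of these subjects have g above 7. The product runs from 30 × 0.10 = 3 to 120 × 0.50 = 60 subjects.

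**The case against.** The strongest reply is that this is the declared estimand at work. The endpoint is abnormalities on treatment, and a value from day 8 or later is not on treatment. The window is arguably generous. If the six half-lives and the 66 hours in protocol 8.5.1 describe the same interval (an inference), one half-life is 66/6 = 11 hours, and 7 days is 168/11, or about 15 half-lives. This stands. A reader might infer that late EOT samples should be moved into the on-DBT tables by their label; that would override the strategy in SAP 3.2, and nothing in the documents calls for it.

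A second reply is that safety information is not lost. This also stands. SAP 6.4.2 lists all results for any subject with a Grade 3 to 4 value at any time point. Protocol 8.2.2 records clinically significant results as AEs, and SAP 6.4.1.6 tabulates follow-up AEs. Protocol 6.3.5 requires immediate evaluation of any positive C-SSRS response, with an AE or SAE if the subject is judged at risk. What is missing is a frequency by arm, with a denominator.

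Third, the sample is the only *scheduled* one. Local results count (SAP 6.4.2), extra tests may be drawn (protocol 6.3.4.1), and subjects stopping for AEs are the likeliest to have them. LFTs and the C-SSRS also have a Week 4 assessment, so the claim of no on-DBT value is confined to haematology and non-LFT chemistry.

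Finally, SAP 7.2 says "refer to the Core SAP for the definitions of analysis periods in Phase 2/3/4 multiple-dose studies with both DBT and OLE Phases", and SAP 6.4 defers further slotting detail to the same source. A special rule for EOT samples could sit there. The visible text shows none.

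**Conclusion.** The gap is real but modest. On the visible rules, an early EOT sample more than 7 days after the last double-blind dose leaves the on-DBT Grade 3 to 4 and shift tables for haematology and non-LFT chemistry and enters no graded-laboratory frequency table. A C-SSRS from the same visit enters no table. The same mechanism applies to early stopping in the OLE, with less effect, because haematology and chemistry are also drawn at Week 14.

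The conclusion assumes that the Core SAP contains no overriding rule for EOT samples and that no unscheduled or local sample fills the gap. The count is unknown; 3 to 60 rests wholly on the assumed rates. The safety summaries are descriptive (protocol 9.3.2), so no hypothesis test is affected.

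Two stronger readings are not supported. One is that the derived EOT value falls back to an earlier sample; that derivation is in the Core SAP. The other is that a Follow-up visit beyond day 28 reaches listings only. In Table 6 the extension is a visit label within the follow-up period, so tables by period, such as AEs and vital-sign abnormalities, are not shown to lose those data.

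**What to change.** Keep the 7-day while-on-treatment tables as the primary safety presentation. In SAP 6.4.2.1 and 6.4.5, add graded-laboratory and C-SSRS frequency tables for the follow-up period in the follow-up safety analysis set, matching what is planned for LFT elevations, vital signs and ECGs. Beside the on-DBT graded table, show by arm the number of treated subjects with no on-DBT haematology or chemistry value.

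The cost is a few more tables with small counts, and their values will reflect time off drug. SAP 8.2 would carry them into the LSLV report. SAP 8.1 limits the follow-up tables in the PCD report, so it needs an added line if they are wanted there.

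Separately, the sponsor should reconcile the protocol's unstated timing of the early EOT visit with the SAP's 7-day window, and confirm from the Core SAP how EOT samples are slotted.
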